After eligibility is confirmed the subject will immediately proceed to the run-in phase. This phase will be completed to ensure complete collection of subject baseline values. Subjects will be instructed not to use any artificial tears for at least 2 hours before testing. They will also be instructed to continue any over-the-counter habitual artificial tears at the same frequency and will be instructed not to change any of their current therapy for their DED. All subjects will undergo a full ophthalmic exam and DED diagnostic testing, which will include clinical evaluations for Dry eye: All sites will perform osmolarity, and Inflammadry test strips for level of MMP-9, staining pattern on cornea (using oxford scale) with Fluorescein, Tear Break Up Time (TBUT), 5 minute Schirmer's testing with anesthesia. USC site will obtain swabs for evaluation of ocular surface microbiome, to be sent to a core facility.

Additionally, clinical photographs of the face, eyes, and meibomian glands will also be collected, and subjects will complete DED questionnaires (SPEED and VAS). All subjects will undergo BBL treatment for a series of 3 treatments after being randomized to treatment protocol 1 or 2 (protocol 1 includes 420nm and 560nm treatment settings, protocol 2 includes only 560nm treatment settings, see Table 2 below). To demonstrate effects of DED treatments, baseline values will later be compared to values following treatment.

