## Broadband Light for Refractory Dry Eye Disease Statistical Analysis Plan

The SPEED validated dry eye disease questionnaire and visual analog scale will be given to patients at time of enrollment and after three sessions, the mean score before and after treatment for all patients will be calculated along with standard deviation and a student's T test will be used to assess whether there is a significant difference ( $p<0.05$ ).

The same will be done for numbers such as tear osmolarity, basal tear production test times, tear break-up times. The proportion of patients in each category of the oxford scale for fluorescein grading (I-V) will also be compared at baseline and post-treatment and the change in grade of individual patients will be assessed descriptively.

For the microbiome portion of the study, swabs from the ocular surface and lid margin will be obtained, in addition to facial skin and environmental control, at baseline and after treatment. 16S ribosomal DNA sequencing will be performed to generate an amplicon sequence variant (ASV) table using DADA2. Briefly, DADA2 performs quality filtering, de-noising, sample inference, and chimera removal using an empiric error model to generate exact amplicon sequences. Next, taxonomies will be assigned to each sequence variant using the RDP naïve Bayes classifier. The 'decontam' R package

(<https://www.biorxiv.org/content/early/2017/11/17/221499>) will be used to remove contaminant sequences based on the composition of negative controls including both DNA extraction buffers and PCR negatives.

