Principal coordinates analysis (PCoA) and permutational multivariate ANOVA will be used to assess for site-dependent effects of treatment on bacterial composition (eyelid margin vs. facial skin vs. environmental control). Alpha diversity will be measured using the Chao1 and Shannon indices, and beta diversity will be measured using Bray-Curtis, Jaccard, and Jenson-Shannon distances. Standard non-parametric methods (e.g. Wilcoxon rank-sum test, Kruskal-Wallis test) will be used to compare alpha and beta diversity metrics between various groups. Zero-inflated negative binomial (ZINB) regression will be used to identify specific bacterial taxa that are differentially abundant by site and treatment. We will also utilize random forest classification as an alternative approach to identify bacterial taxa that distinguish the groups. The Benjamini-Hochberg false discovery rate (FDR) method will be used to adjust all statistical comparisons for multiple hypotheses.

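### Microbiome swabs are repeated within patient, but the SAP states no paired test, patient term or restricted permutation; the error is lost power for time contrasts and can go either way for site contrasts

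*SAP*

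**What the plan says.** The sampling is repeated within patient. The SAP states that "swabs from the ocular surface and lid margin will be obtained, in addition to facial skin and environmental control, at baseline and after treatment". Three of those sources belong to the patient (ocular surface, lid margin, facial skin), so a patient can contribute up to 3 × 2 = 6 linked swabs. The environmental control may not belong to any patient.

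For diversity, the SAP says "Standard non-parametric methods (e.g. Wilcoxon rank-sum test, Kruskal-Wallis test) will be used to compare alpha and beta diversity metrics between various groups". The groups are not defined. It also says that "beta diversity will be measured using Bray-Curtis, Jaccard, and Jenson-Shannon distances", so this metric belongs to a pair of samples, and no step reduces the distances to one value per patient.

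Principal coordinates analysis and PERMANOVA are to be used "to assess for site-dependent effects of treatment on bacterial composition", with the sites given as "eyelid margin vs. facial skin vs. environmental control". ZINB regression is to "identify specific bacterial taxa that are differentially abundant by site and treatment". Random forest classification is the alternative. None of these comes with a patient effect, permutation blocks or patient-level grouping.

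Treatment is not defined as time or as protocol. Both are possible, because Protocol Section 5.1 says "All subjects will undergo BBL treatment for a series of 3 treatments after being randomized to treatment protocol 1 or 2". The same section says that "USC site will obtain swabs for evaluation of ocular surface microbiome"; the number of patients swabbed is not given. Section 3.1 sets a minimum of twenty treated subjects for the study.

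**The concern.** The rank-sum and Kruskal-Wallis tests assume independent observations. Swabs from one patient are not independent, and pairwise distances that share a sample are not independent even when the patients are.

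What goes wrong depends on the contrast, and the SAP does not define the contrasts. A time contrast run unpaired wastes the within-patient information, so a real change may be missed in about twenty patients. A site or protocol contrast that counts repeated swabs as independent can produce false positives. The planned Benjamini-Hochberg adjustment deals with the number of tests; it does not repair p-values computed under a wrong null.

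The PERMANOVA aim also reads as a site-by-time interaction, yet no interaction test and no permutation scheme for one is given.

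**Working it through.** The plan gives no microbiome power, effect size, correlation or sample size, so there is no figure to reproduce. **Assumed throughout:** two-sided 5% before FDR adjustment, n = 20 swabbed patients, within-patient correlation ρ from 0 to 0.7, simulated communities of 40 taxa.

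**1. Time, one value per swab at one site.** With SD 1, an unpaired test takes the variance of the mean difference as 2/n; the true variance is 2(1−ρ)/n. The unpaired test is therefore conservative whenever ρ > 0.

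- Unpaired critical difference: 1.96 × √(2/20) = 0.620.
- True standard error at ρ = 0.3: √(1.4/20) = 0.265. True size is P(|Z| > 0.620/0.265 = 2.34) = 1.9%.
- For a 0.6 SD change, unpaired power is Φ((0.600 − 0.620)/0.265) = 47%. Paired power is Φ(0.6/0.265 − 1.96) = 62%.

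Simulated rank tests, which run a little lower:

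| ρ | Rank-sum | Signed-rank |
|---|---|---|
| 0 | 42% | 41% |
| 0.1 | 42% | 45% |
| 0.3 | 43% | 56% |
| 0.7 | 41% | 89% |

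Rank-sum power stays flat as ρ rises, so what is lost is the gain that pairing would bring.

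**2. PERMANOVA on time at one site.** Power with free against within-patient permutation, over three sets of simulated communities: 35–77% v 34–75% at ρ = 0, 15–67% v 44–90% at 0.3, and 1–36% v 78–100% at 0.7. The direction is consistent; the size depends heavily on the community model.

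**3. Site contrast with both time points included.** Let p, s and e be the patient, patient-by-site and residual variances. Each patient-site has two swabs. The true variance of a difference between two site means is (2s + e)/n, because the patient effect cancels. Treating 2n swabs per site as independent gives (p + s + e)/n. With p + s + e = 1, the ratio of true to assumed variance is 1 + s − p. The naive analysis is therefore anti-conservative if s > p and conservative if s < p.

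Null rejection by freely permuted PERMANOVA (two sites, two times, Bray-Curtis):

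| p / s | Ratio | Rejects |
|---|---|---|
| 0.1 / 0.3 | 1.2 | 12–13% |
| 0 / 0.3 | 1.3 | 19–20% |
| 0.1 / 0.5 | 1.4 | 27–29% |
| 0.3 / 0.3 | 1.0 | 3–6% |
| s = 0 | below 1 if p > 0 | 0.3% |

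Blocking on patient alone does not cure this. Shuffling all swabs freely within patient rejects 22–53% when patient-by-site variance is present; moving each site's two swabs together rejects 4–6%. For alpha diversity with three sites and two times, a patient-only block test rejects 11–19%, against 6–12% for Kruskal-Wallis.

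**4. Site contrast at one time point (alpha diversity, site means 0, 0.3 and 0.6 SD).** Power for Kruskal-Wallis, Friedman and a patient-block model: 35/28/36% at ρ = 0, 30/38/49% at 0.3, and 20/72/86% at 0.7.

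**5. Site-by-time interaction.** In a simulation with two sites and a change at one of them, free against within-patient permutation has power 50% v 48% at same-site correlation 0, 25% v 60% at 0.3, and 2% v 96% at 0.7.

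**6. Raw pairwise distances, conditional on their being ranked.** Twenty samples give 20 × 19/2 = 190 distances, and each sample enters 19 of them. Under a true null, a rank-sum test of baseline-baseline against post-post distances rejects about 40–50% (separate simulations span 37–53% for Bray-Curtis and up to 58% for Jaccard). Comparing within-time with between-time distances rejects 0–3.5%. A rank test with labels permuted within patient rejects 3–6%.

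**7. Protocol 1 against 2, with m swabs per patient pooled as independent.** The variance inflation is 1 + (m−1)ρ. At ρ = 0.5 it is 1.5 for m = 2 and 3.5 for m = 6. The size is P(|Z| > 1.96/√1.5 = 1.60) = 11% and P(|Z| > 1.96/√3.5 = 1.05) = 29–30%. Simulated rank-sum rates with 10 patients per protocol are 12% and 30%.

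**The case against.** The strongest reply is that the SAP does not commit to any of these mistakes. The rank tests are introduced as examples, so signed-rank and Friedman tests are not excluded. PERMANOVA is named for composition. If one of the undefined comparisons is protocol 1 against protocol 2 with one value per patient, rank-sum is a correct choice. All of that stands. It means that the plan leaves the choice open, and the choices left open have error rates from near zero to about one half.

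Two stronger readings are tempting. A reader might infer that about half of null studies will show a significant diversity change. That follows only if raw distances are ranked in one particular way, which the SAP nowhere says. A reader might also infer that ignoring pairing is always conservative. That holds for time with one value per swab and for PERMANOVA on time, but not for site contrasts that use both time points, nor for raw distances or pooled protocol comparisons.

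It is also fair to say that the microbiome work is outside the hypothesis in Protocol Section 2.1, that only one named site takes the swabs, and that every rate above rests on assumed values. This limits the weight of the point. Formal tests with FDR control are still planned, so p-values will be reported.

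**Conclusion.** The point holds as an unaddressed dependence between swabs, at modest weight. That swabs repeat within patient while no paired or patient-level method is stated can be read directly from the SAP and depends on no assumption.

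The consequences differ by contrast. Time contrasts with one value per swab, and PERMANOVA on time, forgo power at moderate correlation: about 42% against 56% at 0.3 and 42% against 90% at 0.7 for alpha diversity, and nothing near zero. Site contrasts with both times can err either way, with null rejection of about 0–29% under the assumed variances. False positives rise if protocols are compared with swabs pooled. The 40–50% rate for raw distances is conditional on a procedure that the SAP does not state.

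The direction of each error follows from the variance arithmetic. The rates are only as good as the assumed correlations, variances, effect sizes and 20 swabbed patients.

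**What to change.** Define each contrast, its unit, and whether treatment means time or protocol. Then state:

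- **Alpha diversity, time:** signed-rank test at each patient site.
- **Alpha diversity, across patient-linked sites:** use one time point, or one baseline-to-post change per patient-site, with a patient-block model or Friedman test. If both times enter, use a mixed model with patient and patient-by-site effects.
- **Composition (PERMANOVA):** for time, swap baseline and post labels within patient and site. For site, move each site's two swabs together as a block within patient. For protocol, permute whole patients. For site-by-time, test each patient's baseline-to-post changes with within-patient sign flips or restricted permutation.
- **Distances:** no ordinary rank-sum or Kruskal-Wallis test on raw pairwise distances. Use permutation-based tests, or one distance per patient (per site) for protocol comparisons. Such a distance measures the size of change, not its direction, and cannot test time itself.
- **ZINB:** a patient effect, plus patient-by-site when both times and several sites are modelled, with a pre-stated paired per-taxon test as fallback.
- **Random forest:** resampling grouped by patient.
- **Environmental controls:** analyse separately unless each is linked to a patient visit.

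The cost is SAP wording and slightly more analysis, with no new samples. If within-patient correlation is near zero, there is no power gain, and Friedman loses a little (28% against 35% for Kruskal-Wallis at correlation 0). ZINB with patient effects may not converge for sparse taxa, which is why the fallback is needed.
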